13.3. Analysis of investigational products

For each infusion, the following information will be reported by study group for all randomized patients:

1. Receipt of infusion 1, number (%)
2. Receipt of infusion 2, number (%)
3. Receipt of infusion 1 within time window (see Section 9), number (%)
4. Receipt of infusion 2 within time window (see Section 9), number (%)
5. Reason for not receiving infusion 1
6. Reason for not receiving infusion 2
7. Zoledronic acid as infusion 1, number (%)
8. Zoledronic acid as infusion 2, number (%)
9. Placebo as infusion 1, number (%)
10. Placebo as infusion 2, number (%)
11. Receipt of vitamin D loading dose prior to infusion 1, number (%)
12. Receipt of vitamin D loading dose prior to infusion 2, number (%)
13. Time from receipt of vitamin D loading dose 1 to infusion 1, days
14. Time from receipt of vitamin D loading dose 2 to infusion 2, days
15. Time from randomization to infusion 1, days
16. Time from randomization to infusion 2, months
17. Duration of infusion 1, minutes
18. Duration of infusion 2, minutes
19. Interruption of infusion 1, number (%)
20. Interruption of infusion 2, number (%)
21. Reason for interruption of infusion 1
22. Reason for interruption of infusion 2

Study Name: The Fragility Fracture Trial
Version No: 2
Date: 2020-10-04
EudraCT No: 2019-004766-17

The numeric variables will be summarized using means, medians, standard deviations, 25th percentiles, 75th percentiles, minimums, and maximums. The categorical variables will be summarized as number and percent in each level. The number and percent with missing values will be calculated for all variables.

13.4. Analysis of follow-up

The number and percent of randomized patients that are contacted at each study contact (visits and telephone interviews) will be reported for the zoledronic acid and placebo groups. The number and percent not completing follow-up will be presented by cause (death, adverse event, loss to follow-up, withdrawal, etc.). Differential follow-up duration between the zoledronic acid and control group will be examined by plotting Kaplan-Meier curves and testing for a difference using the log-rank test. Differences in the number and percent prematurely unblinded will be examined using Fisher's exact test. Number and percent prematurely unblinded by cause (accident, adverse event, or other) will be presented.

13.5. Analysis of concomitant medications

The number and percent of participants receiving an osteoporosis medication (other than the assigned zoledronic acid) during follow-up will be reported. The study groups will be compared using Fisher's exact test. The number and percent reporting use of vitamin D supplements at the required monthly dose will be presented for each study contact. The number and percent reporting complete adherence to vitamin D (i.e. use at every contact) will also be calculated and compared between the groups using Fisher's exact test.

13.6. Efficacy analysis

All randomized patients with non-missing outcome data will be included in an efficacy analysis. For time-to-event outcomes, survival time will be calculated as date of event minus date of randomization plus 1 day (to account for the possibility of an event occurring later in the day of randomization). For participants not experiencing the event, time-to-event will be set as the follow-up time (see definition above). If the date of a participant's time-to-event outcome is incomplete, the date will be imputed as was done in a previous trial.²⁰ Thus, if the day of the month is missing, it will be imputed as the 15th. If both the day and the month are missing, these will be imputed as July 1. If the entire date is missing, the time-to-event will be set to 1 day. Events that cannot be verified through registries or medical record review will be excluded, but the number and proportion of events not verified will be reported.

For time-to-event outcomes, 4-year cumulative incidence curves will be estimated using the Kaplan-Meier method. Number of persons with an event, numbers of events, and incidence

Study Name: The Fragility Fracture Trial
Version No: 2
Date: 2020-10-04
EudraCT No: 2019-004766-17

rates (number of events/total person-years at risk of first event) will also be provided. The efficacy of zoledronic acid will be determined on the basis of the log-rank test. The relative effect of zoledronic acid versus placebo will be represented by hazard ratios (with 95% confidence intervals), estimated using Cox regression. These models will not be adjusted for covariates in the main analysis, so as to be comparable to the log rank test. The proportional-hazards assumption will be assessed using log-minus-log plots and by Wald tests of treatment-by-time product terms. In the case of a clear violation of this assumption, hazard ratios will be computed for time-intervals in which hazard ratios are more stable (e.g. 6-month or 12-month periods). As an additional analysis, the number of participants needed to treat for 4 years to prevent one fracture will be estimated for each fracture outcome using Kaplan-Meier estimated risks. Ninety-five percent confidence intervals will be provided for numbers needed to treat,^{59,60} with variance estimates derived using the method proposed by Kalbfleisch and Prentice (p. 18).⁶¹

The occurrence of falls will be analyzed as the number and percent of participants reporting at least one fall. Falls will not be analyzed as a time-to-event outcome because participants may not remember exactly when they fell. The zoledronic acid and placebo groups will be compared using relative risks, with 95% confidence intervals estimated based on the normal approximation. Participants with incomplete follow-up and who did not report a fall during follow-up will be assumed not to have fallen.

Change-from-baseline outcomes will be analyzed using analysis of covariance. The response variable will be post-intervention value and the explanatory variables will be baseline value and treatment group. For the EQ-5D-5L exploratory outcomes, which will be measured every 12 months of follow-up, an analysis of covariance will be run with each follow-up value as the post-intervention value. To prevent the problem of multiple testing, the stepwise approach to testing described in Section 13.8 will be used. The assumptions of linearity, constant variance, and normality will be checked using residual plots and normal quantile-quantile plots. Clear violations of these assumptions will be dealt with by transformations of the response variable or its baseline value. Clear violations of the assumption of constant variance may instead be dealt with using the method of weighted least squares. Outliers will not be removed. Participants with missing follow-up data on change-from-baseline variables will be excluded.

The hypothesis tests of efficacy will not be adjusted for multiple testing to avoid a large reduction in the power of the trial.

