7.1. Primary outcome

Due to the high clinical relevance of most fractures, the primary outcome will be time to first new clinical fracture (ICD-10-SE codes: S12-S52, S72, S82, M48.5, M49.5, M80.0A, M80.0J, and M80.0K). Clinical fracture will be defined as any fracture that comes to medical attention, excluding fractures of the facial bones, skull, hands, and feet (ICD-10-SE codes: S02, S62, and S92), which are not generally considered osteoporotic.¹⁰ For the same reason, pathological fractures (e.g., due to cancer or osteomyelitis) will be excluded. High-energy fractures will be included because these are also associated with low bone mineral density.^{11,43}

Participants will be asked about fractures at study contacts, which will take place every 6 months of follow-up (see Section 9). Participants will also have the possibility of reporting fractures to their study center between the scheduled contacts. Participants who withdraw will be asked if they wish to answer questions about incident fractures before they formally withdraw. The Swedish Fracture Register will also be used to trace fractures for patients who consent to registry follow-up.

Fractures identified through interview will be verified through review of medical records by the study site investigator, given that the participant consents to it. Due to limited resources, the sponsor/coordinating investigator will not adjudicate fractures or other outcomes. To reduce the amount of missing data in the 10-year post-study analysis, fractures will be traced centrally by the sponsor using the above-mentioned ICD-10-SE codes in the Swedish National Patient Register. This register records all diagnoses made in inpatient care in Sweden since 1987 and all outpatient secondary (i.e., non-primary) care since 2001.⁴⁴

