13.8. Subgroup, sensitivity, and exploratory analyses

Baseline characteristics and efficacy outcomes will be presented in subgroups defined by type of baseline fragility fracture (grouped by the first 3 characters of ICD-10-SE codes), age (65-74, 75-84, or ≥ 85 year), sex, study center, and FRAX 10-year probability of major osteoporotic fracture. In the efficacy analysis, product terms will be included in regression models to assess interaction of treatment with time since fragility fracture, type of fragility fracture, age, sex, study center, physical activity (mean steps/day), and receipt of one or both infusions. These interaction effects will be tested using Wald tests for numeric and binary variables and likelihood ratio tests for multi-level categorical variables. We do not expect these interaction analyses to show significant differences in effect.

Six sensitivity analyses will be conducted. First, to assess the presence of confounding, regression analyses will be adjusted for the following baseline covariates: age, sex, BMI, study center, time since fragility fracture, and site of fragility fracture (grouped by the first 3 characters of ICD-10-SE code). Second, the efficacy analysis will be rerun in a per-protocol population (i.e., participants who met all eligibility criteria, either died or completed follow-up, and both were qualified to receive and did receive the 2 assigned infusions). Third, efficacy concerning time-to-event outcomes will be analyzed using the Andersen-Gill Cox model for recurrent events.⁶³ Fourth, in the analysis of the primary outcome, the potential effect of informative censoring (including the competing risk of death) will be assessed by rerunning Cox models under the extreme scenarios that all participants who did not complete follow-up either (1) sustained a fracture at the time of censoring (i.e., were at high risk of fracture) or (2) had complete follow-up with no event (i.e., were at low risk of fracture).⁶⁴ Fifth, participants with a history of cancer at baseline will be excluded from the efficacy analysis of new cancers diagnosed during follow-up. Sixth, outcome events not verified by medical records will be included in the efficacy analyses.

Study Name: The Fragility Fracture Trial
Version No: 2
Date: 2020-10-04
EudraCT No: 2019-004766-17

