To assess the time-to-onset of treatment effect on the primary outcome, Kaplan-Meier curves will be compared using the log-rank test with censoring at months 48, 42, 36, and so on until month 6. To avoid the problem of multiple testing, a fixed-sequence procedure will be used in which the test will first be performed for risk at month 48, then at month 42, and so on until month 6.⁶⁵ If a p-value ≥ 0.05 is obtained, the results of all subsequent tests will also be considered non-significant. Similarly, Cox regression will be used to estimate hazard ratios and 95% confidence intervals, with censoring at month 48, 42, and so on until month 6.

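### The date-imputation rules in section 13.6 put undated events on day 1 and have no bounds, so a few events get impossible or misplaced times; the primary 48-month test is essentially unaffected

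*Protocol*

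**What the plan says.** Protocol section 13.6 defines the time scale: "survival time will be calculated as date of event minus date of randomization plus 1 day". The smallest valid value is therefore 1.

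Three imputation rules follow, attributed to a previous trial:

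- Day missing: "if the day of the month is missing, it will be imputed as the 15th".
- Day and month missing: "If both the day and the month are missing, these will be imputed as July 1".
- Nothing known: "If the entire date is missing, the time-to-event will be set to 1 day".

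No floor at randomization and no ceiling at death or last contact is given, and the contact schedule is not used. Yet section 7.1 states: "Participants will be asked about fractures at study contacts, which will take place every 6 months of follow-up". Table 1 in section 9 lists outcome assessment at 6, 12, 18, about 24, 30, 36, 42 and 48 months.

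Two further provisions decide which events are exposed. Section 13.6 adds: "Events that cannot be verified through registries or medical record review will be excluded". Section 13.8 brings such events back: "Sixth, outcome events not verified by medical records will be included in the efficacy analyses".

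The analysis most sensitive to early event times is in section 13.8: "Kaplan-Meier curves will be compared using the log-rank test with censoring at months 48, 42, 36, and so on until month 6". The cuts are tested in that order and claims stop at the first non-significant result.

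**The concern.** The day-1 rule discards information that the trial collects. A fracture first reported at the 42-month contact, after none was reported at 36 months, lies between those two contacts. The rule dates it to the day of randomization, before several contacts at which the participant reported no fracture. A day-1 event then counts in every truncated analysis down to month 6.

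The other two rules can date an event before randomization, where the protocol's own formula returns zero or a negative number. They can also date it after the end of follow-up as section 13 defines it, so that a real event drops out of the 4-year estimate. No handling is stated for either case.

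At stake are individual survival times, person-years, the early part of the Kaplan-Meier curves, the 6- or 12-month hazard ratios planned if proportional hazards fails, and the time-to-onset analysis. The recall problem is real: section 13.6 declines to analyse falls as time-to-event because participants may not recall the dates.

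**Working it through.** **Inputs.** From the protocol: the formula and rules in 13.6; recruitment from the first quarter of 2021 to the last quarter of 2022 and 4 years of follow-up each (section 4); 2900 participants, 227 events, hazard ratio (HR) 0.65, placebo 4-year risk 10%, 5% dropout, 90% power, two-sided 5% (section 13.10, Appendix 1). Not in the protocol: the share of events with missing dates, so 0% to 10% is an assumed range.

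**1. The plan's own base figure.** 4 × (1.960 + 1.282)² / ln(0.65)² = 226.5, so 227 events. Risk under treatment: 1 − 0.90^0.65 = 0.06619. 227 / 0.083096 = 2732, and 2732 / 0.95 = 2876, rounded to 2900. All reproduced.

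**2. Date arithmetic** (event date − randomization date + 1).

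| Randomized | True fracture | Known part | Imputed | Time by the rule | True time |
|---|---|---|---|---|---|
| 20 Mar 2021 | 25 Mar 2021 | year, month | 15 Mar 2021 | −4 | 6 |
| 15 Oct 2021 | 20 Nov 2021 | year | 1 Jul 2021 | −105 | 37 |
| 1 Mar 2021 | 10 Feb 2025 | year | 1 Jul 2025 | 1584 | 1443 |

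In the third case the 48-month point is day 1462.

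**3. How often.** Let randomization fall at a uniform fraction u of the year, with a constant event rate. Events in the calendar year of randomization are proportional to ∫₀¹(1 − u)du = 0.5. Those with July 1 before randomization are proportional to the same integral over u > 0.5, which is 0.125. The share is 0.125/0.5 = 25%. Over 4 years, 0.125/4 = 3.1% of all year-only dates. The same argument at the other end gives 3.1% after month 48.

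Simulation of 400,000 dates gives 3.2% with time 0 or less and 3.1% after month 48. About 50% land in the wrong 6-month interval. For the 15th-of-month rule, 0.3% have time 0 or less.

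**4. Counts under an assumed share.** If 2% to 5% of 227 events were wholly undated, 4.54 to 11.35 would move to day 1, against about 227 × 0.98 × 6/48 = 27.8 (or 227 × 0.95 × 6/48 = 27.0) dated events before month 6. If instead 2% to 5% were year-only, the expected number with time 0 or less is 0.032 × 4.54 = 0.15 to 0.032 × 11.35 = 0.36 in the whole trial.

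**5. Effect on the tests.** Simulated with 2900 participants, 1:1 allocation, 10% placebo risk, 5% dropout, and missing dates independent of arm.

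- HR 0.65 throughout: with 0% to 10% undated, month-48 power is 0.90 to 0.92 and the median HR 0.65 to 0.66. Events by month 6 rise from 30.8 to 41.5 at 5% and 51.8 at 10%.
- No effect at any time: month-48 rejection is 0.042 to 0.053 and month-6 rejection 0.045 to 0.057.
- Delayed effect (HR 1 for months 0 to 12, then (0.65 × 48 − 12)/36 = 0.53):

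| Undated | Rule | Events by month 6 | Month-6 HR | Month-6 rejection | Month-48 power |
|---|---|---|---|---|---|
| 0% | none needed | 37.6 | 1.00 | 0.047 | 0.903 |
| 1% | day 1 | 39.6 | 0.96 | 0.057 | 0.892 |
| 1% | midpoint | 37.8 | 1.00 | 0.050 | 0.896 |
| 5% | day 1 | 47.3 | 0.90 | 0.062 | 0.897 |
| 5% | midpoint | 37.6 | 1.00 | 0.043 | 0.895 |
| 10% | day 1 | 57.4 | 0.84 | 0.097 | 0.897 |
| 10% | midpoint | 37.7 | 1.00 | 0.050 | 0.893 |

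HRs are medians. The standard error of a rejection rate near 5% is about √(0.05 × 0.95/3000) = 0.004 (3,000 trials per setting; 1,500 for the first row). The rates are for the single cut, before the fixed-sequence gate. The distortion arises because later events, carrying a later effect, are moved into the early window.

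**The case against.** The strongest reply is that few events are exposed. An event counted in the main analysis must be confirmed by a register or medical record, which will normally carry a date. A wholly undated share near 0% is at least as plausible there as 2% to 5%. Section 12.5 also provides for range and logical checks with queries to centers, which should recover some dates. The time-to-onset question is labelled exploratory in section 3.3, and month 6 can be claimed only if all seven later cuts are significant. Bounding an imputed date is often left to a statistical analysis plan, and the rule follows a previous trial.

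Most of this stands as to size. It does not remove the point. The protocol does not leave the matter open: it fixes a rule that, followed literally, returns impossible values. Data checks reduce the number of missing dates but do not change what happens to those that remain. Precedent does not make a negative time valid. The verification requirement gives no protection in the sensitivity analysis that admits unverified events, although that those events lack dates more often is an inference, not something the protocol states.

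A reader might infer that the primary comparison, or all eight time-to-onset tests, are compromised. The figures do not support that: the month-48 test keeps its power and its type I error even at 10% undated, provided that missing dates do not depend on arm. A reader might also take the 25% as a share of all year-only dates. It applies only to those in the calendar year of randomization.

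**Conclusion.** The rules are wrong as written, for a small number of events. Out-of-range times affect about 3% of year-only dates at each end, probably less than one event with a negative time in the whole trial. The day-1 default is the larger distortion, because it can shift an event by up to 4 years and always toward the start.

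Its effect is confined to early cuts of the exploratory time-to-onset analysis, interval hazard ratios, curve shape and the sixth sensitivity analysis. At 1% to 5% undated with a delayed effect, the month-6 HR is pulled from 1.00 to 0.96 to 0.90, while rejection stays at about 0.06. The larger figures at 10% are an upper illustration.

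This rests on uniform recruitment over the calendar year, a constant event rate for the date shares, missingness unrelated to arm, and an assumed share of undated events. The point is a minor to moderate correction and no threat to the primary result.

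**What to change.** In section 13.6, replace the day-1 default and bound the other two rules:

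- **Interval.** It starts at the last contact without the event, or at randomization if there is none. It ends at the earliest of the contact or record at which the event was reported, death, and end of follow-up.
- **Known date parts.** Restrict the interval further to the known month or year.
- **Imputed date.** Use the midpoint of what remains, so that no time is below 1 day or beyond follow-up.

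Applied to the three cases above:

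- 20 to 31 March 2021 gives day 6 (true 6).
- 15 October to 31 December 2021 gives day 39 (true 37).
- With no event reported at 42 months and the report at 48 months, 1 January to 1 March 2025 has midpoint 30 January. That gives 1461 − 30 + 1 = day 1432 (true 1443).

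The cost is a sentence or two in 13.6, and making sure that every contact date is captured. Section 12.2 says that the eCRF does not yet exist, so this can be built in. There is a small downside: imputed times cluster at interval midpoints, and a missed contact widens the interval. With contacts on schedule the error for an undated event is at most 3 months. If neighboring contacts use opposite ends of their ±4-week windows, it is at most half of 6 months plus 8 weeks, that is 3 months plus 4 weeks.

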12.5. Data management

The trial statistician will continuously monitor eCRFs for accuracy and completeness (including range and logical checks) and for compliance with this protocol. Any inaccuracies, inconsistencies, or deviations will be reported to the appropriate study center, with a request for a correction or an explanation. The trial database will be backed up regularly. The sponsor/coordinating investigator may also appoint staff to conduct on-site monitoring to verify eCRFs with source documents. A detailed plan for data management has not been developed at the time of writing, but it will be attached to the Clinical Study Report.

13. Statistical Analysis

Statistical analyses will be performed using the latest version of R software. All statistical hypothesis tests that can be two-sided will be two-sided. P-values <0.05 will be considered statistically significant, unless otherwise specified. P-values will be rounded to two decimal places if ≥ 0.01 and rounded to three decimal places if <0.01 but ≥ 0.001 . P-values <0.001 will be expressed as " <0.001 ".

The zoledronic acid and placebo groups will be defined according to randomization. Baseline date will be defined as the date of randomization. Follow-up time will be defined as the date of death, withdrawal, loss to follow-up, or last follow-up contact (whichever came first) minus the date of randomization plus 1 day (to account for the possibility of an event later in the day of randomization). Incomplete follow-up will be defined as follow-up time that ends before the last study contact.

Study Name: The Fragility Fracture Trial
Version No: 2
Date: 2020-10-04
EudraCT No: 2019-004766-17

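### Kaplan-Meier with death censored overstates the 4-year risks of outcomes other than death and makes the fracture NNTs modestly too favourable; the incidence rate needs a separate clarification

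*Protocol*

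**What the plan says.** Four statements in the protocol combine.

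- Section 13 (opening text): "Follow-up time will be defined as the date of death, withdrawal, loss to follow-up, or last follow-up contact", whichever comes first.
- Section 13.6, participants without the event: "For participants not experiencing the event, time-to-event will be set as the follow-up time (see definition above"). For every time-to-event outcome except death itself, a participant who dies event-free is therefore censored at death.
- Section 13.6, estimator: "For time-to-event outcomes, 4-year cumulative incidence curves will be estimated using the Kaplan-Meier method".
- Section 13.6, NNT: the "number of participants needed to treat for 4 years to prevent one fracture will be estimated for each fracture outcome using Kaplan-Meier estimated risks".

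Death as a competing risk is named once, in the fourth sensitivity analysis of Section 13.8. That analysis reruns Cox models for the primary outcome under two extremes for everyone who did not complete follow-up. In the first they fracture at the moment of censoring; in the second they stay event-free to the end.

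On incidence rates, Section 13.6 lists persons with an event and numbers of events as separate items, and then says that "rates (number of events/total person-years at risk of first event) will also be provided". Section 13.8 also plans that "efficacy concerning time-to-event outcomes will be analyzed using the Andersen-Gill Cox model for recurrent events", so repeat events will be collected.

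**The concern.** When death is censored, the Kaplan-Meier complement answers a hypothetical question: how many would fracture by 4 years if death were removed. Cumulative incidence in the ordinary sense counts those who fracture before dying, and it cannot be larger. Participants are 65 or older with no upper age limit, and Section 13.8 has a subgroup aged 85 or over, so some deaths before fracture are certain. Reduction of death is also a secondary objective, so the protocol itself allows that mortality may differ between arms.

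Absolute risks and NNTs are the figures most likely to be carried into guidelines and cost arguments; Section 17 already argues from a hip-fracture NNT. A bias that leans towards the drug matters there even when it is small.

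The rate definition is a different defect. If all events are counted but the person-time clock stops at the first, the rate matches neither a first-event analysis nor a recurrent-event analysis.

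**Working it through.** **Inputs from the protocol.** Placebo 4-year fracture risk 10% and hazard ratio 0.65 (Section 13.10, Appendix 1); 1:1 allocation of 2900, so 1450 per arm (Sections 10 and 13.10).

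**Assumed.** Constant hazards; 4-year mortality m of 5 to 20%, equal in both arms unless stated. The protocol gives no mortality figure, and its 5% dropout excludes deaths.

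**The protocol's own figures.** Required events: 4 × (1.960 + 1.282)² / ln(0.65)² = 226.5, i.e. 227. Risk on zoledronic acid: 1 − 0.9^0.65 = 0.06619. Participants: 227 / [(0.10 + 0.06619)/2] = 2732; divided by 0.95, 2876. All agree with Appendix 1.

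**Kaplan-Meier NNT.** 0.10 − 0.06619 = 0.03381; 1/0.03381 = 29.6.

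**Competing-risk NNT.** Fracture hazard λ = −ln(0.9)/4 = 0.02634 per year on placebo, and 0.65 × λ = 0.01712 on drug. Death hazard μ = −ln(1 − m)/4. Cumulative incidence = λ/(λ + μ) × [1 − exp(−4(λ + μ))].

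| 4-year mortality (assumed) | Placebo | Drug | Difference | NNT |
|---|---|---|---|---|
| none (= Kaplan-Meier) | 10.00% | 6.62% | 3.38 points | 29.6 |
| 5% | 9.75% | 6.45% | 3.30 | 30.3 |
| 10% | 9.50% | 6.29% | 3.21 | 31.1 |
| 15% | 9.24% | 6.11% | 3.13 | 32.0 |
| 20% | 8.98% | 5.94% | 3.04 | 32.9 |

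Relative to the competing-risk figure, Kaplan-Meier overstates the placebo risk by 2.5% at 5% mortality (10.00/9.75) and by 11% at 20% (10.00/8.98).

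**If mortality differs by arm (assumed death hazard ratios).** At 0.8 the NNT is 31.8 with 10% placebo mortality and 34.3 with 20%. At 1.1 it is 30.8 and 32.2. The direction stays the same unless the drug raises mortality markedly; with 10% placebo mortality and a death hazard ratio of 1.5, the competing-risk NNT is 29.7, about the Kaplan-Meier value.

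**If 10% is instead the actual cumulative incidence.** The competing-risk NNT is then about 29.6, and Kaplan-Meier would report 28.9, 28.2, 27.4 or 26.7 at 5, 10, 15 or 20% mortality. The gap is of similar size.

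**Hip fracture** (457/10,361 = 4.4%, Section 13.10; hazard ratio 0.65): Kaplan-Meier NNT 65.7, against 67.4 at 5% mortality and 73.2 at 20%.

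**Sampling error.** The standard error of the 3.38-point difference with 1450 per arm is √(0.10 × 0.90/1450 + 0.0662 × 0.9338/1450) = 1.02 points. The 95% interval is 1.38 to 5.39 points, an NNT of about 19 to 73.

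**Incidence rate.** The first-event rate on placebo is 2.63 per 100 person-years. If participants with a fracture average 1.1 to 1.3 fractures (assumed), all events over first-event person-time gives 2.63 × 1.1 = 2.90 to 2.63 × 1.3 = 3.42, i.e. 10 to 30% higher.

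**The case against.** The best defence has four parts.

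1. *The protocol already addresses competing death.* It does so in part. A reader might infer from "sustained a fracture at the time of censoring (i.e., were at high risk of fracture") that every death is simply scored as a fracture. The text does not support that reading, because the second scenario keeps the same participants event-free to the end, which resembles competing-risk handling of death. Death is therefore bracketed from both sides. But the check yields only hazard ratios, covers only the primary outcome, and treats withdrawals exactly as it treats deaths. It corrects no curve, no NNT and no secondary outcome.
2. *The effect is small and the mortality is assumed.* This stands. Participants are ambulatory and community-dwelling, and those with a life expectancy under a year are excluded, so the upper end of the mortality range has no support in the protocol. At 5 to 10% the NNT moves by 0.7 to 1.5.
3. *The NNT is an additional analysis, and persons with an event are reported*, so a reader could compute crude proportions. True, but those proportions also count withdrawals as event-free, and the headline curves and NNTs would remain as specified.
4. *The rate may simply be a loosely worded first-event rate.* This is possible. Counting all events is the literal reading but not the only one.

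Two further inferences should be resisted. The rate wording does not make the NNT too favourable, because the NNT comes only from Kaplan-Meier risks. Nor can the 10% planning risk be said to have deaths in its denominator: Section 13.10 does not say how deaths among the 10,361 people were handled.

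**Conclusion.** The point holds as a correctable choice of estimator for descriptive results. For all time-to-event outcomes except death, the planned cumulative incidence is overstated. The clinical-fracture NNT is too low by about 0.7 to 3.3 over an assumed 5 to 20% mortality equal in both arms, and by more if the drug also lowers mortality. This rests on constant hazards and on mortality figures that the protocol does not supply, and it is well inside the sampling error of the NNT. It would not support a claim that the trial's efficacy conclusion is biased: the log-rank test, the cause-specific hazard ratio, the 227 events, the power and the time-to-death analysis are all unaffected.

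The incidence-rate wording is a separate, smaller matter. Taken literally it mismatches numerator and denominator; if first events were meant, a clarifying phrase settles it.

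**What to change.** - **Section 13.6, estimation.** Keep the log-rank test and the cause-specific Cox model. For every time-to-event outcome except death, estimate cumulative incidence with the Aalen-Johansen estimator, death competing, and derive risk differences, NNTs and their confidence intervals from it, with the variance that belongs to that estimator. Kaplan-Meier remains right for time to death.
- **Section 13.8, fourth sensitivity analysis.** Apply the two extreme scenarios to dropouts only, and treat death as a competing event.
- **Section 13.6, incidence rate.** Define it as first events over person-years to first event. If a recurrent-event rate is wanted, add a second one: all events over total person-years.

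The cost is a few sentences and standard R functions. No new data are needed, since deaths are already collected. The downside is a slightly less favourable NNT. The change should be made before the randomization list is unlocked.
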